10. CONCOMITANT TREATMENT

10.1. Supportive Care Guidelines

Patients should be advised to inform their study doctor of all concomitant medications, including over-the-counter medications and dietary supplements.

All concomitant medications taken within 28 days prior to first dose of study drug treatment and during the clinical trial (up to 30 days post-treatment) must be recorded on the appropriate Case Report Form.

Subjects are permitted the use of corticosteroids with minimal systemic absorption (e.g. topical, ocular, intra-articular, intranasal, and inhaled).

Adrenal replacement steroid doses including doses > 10 mg daily prednisone are permitted.

A brief (less than 3 weeks) course of corticosteroids for prophylaxis (e.g. contrast dye allergy) or for treatment of non-autoimmune conditions (e.g. delayed-type hypersensitivity reaction caused by a contact allergen) is permitted.

Patients should receive appropriate supportive care measures as deemed necessary by the treating investigator including but not limited to the items outlined below:

- **Diarrhea**: All patients who experience diarrhea should be advised to drink liberal quantities of clear fluids. If sufficient oral fluid intake is not feasible, fluid and electrolytes should be substituted via IV infusion.
- **Nausea/Vomiting**: Nausea and vomiting should be treated aggressively, and consideration should be given in subsequent cycles to the administration of prophylactic antiemetic therapy according to standard institutional practice. Patients should be strongly encouraged to maintain liberal oral fluid intake.
- **Anti-infectives**: Patients with a documented infectious complication should receive oral or IV antibiotics or other anti-infective agents as considered appropriate by the treating investigator for a given infectious condition, according to standard institutional practice. Prophylactic administration should be considered for the cases outlined in Section 11.
- **Anti-inflammatory or narcotic analgesics** may be offered as needed. Acetaminophen/paracetamol to a maximum total daily dose of 2 g is permitted. Daily intake over 2 g is prohibited.
- Patients who need to be on anticoagulant therapy during treatment should be treated with low molecular weight heparin. Monitoring of prothrombin time/international normalized ratio (PT/INR) should be performed as appropriate.

10.2. Prohibited and/or Restricted Medications and Therapies

Patients are prohibited from receiving the following therapies during the treatment phase of this trial:

- Immunotherapy or immunosuppressive drugs (i.e. chemotherapy or systemic corticosteroids) except for short-term treatment of allergic reactions or for the treatment of an immune-related adverse event (irAE). Short-term administration of systemic steroids (e.g. for allergic reactions or the management of irAEs) is allowed. Topical and inhaled steroids are allowed.
- Systemic corticosteroids > 10 mg daily prednisone equivalent, except as stated in Section 10.1 or to treat a drug-related AE (e.g. Section 11).
- Growth factors (granulocyte colony-stimulating factor or granulocyte-macrophage colony stimulating factor) are prohibited.
- Vaccination within 28 days of the first dose of avelumab and while on study is prohibited, except for administration of inactivated vaccines (for example, inactivated influenza vaccines).
- Bisphosphonate or denosumab treatment is not allowed unless it has been initiated more than 14 days prior to receiving the first administration of avelumab.
- Anti-cancer systemic chemotherapy or biological therapy or investigational agents other than avelumab.
- Surgical resection of tumor.
- Other experimental pharmaceutical products.
- Herbal remedies reasonably known to have immunostimulating properties (e.g. mistletoe extract) or reasonably known to potentially interfere with major organ function (e.g. hypericin).

There are no prohibited therapies during the Post-Treatment Follow-up Phase.

10.3. Clarifications about Steroid Use

Data indicate that corticosteroids have an adverse effect on T cell function and that they inhibit and damage lymphocytes.^{44,45} Furthermore, as with all immunotherapies intended to augment cell-mediated immunity, there is a risk that concomitant immunosuppressives such as steroids will counteract the intended benefit of the proposed study treatment. However, studies with anti-CTLA-4 compounds indicate that short-term use of steroids may be employed without compromising clinical outcomes.⁴⁶

Therefore, the use of steroids during this trial is restricted as follows:

- **Therapeutic use:** For treatment of infusion-related reactions and short-term treatment of immune-related adverse events (irAEs), steroids are permitted according to the modalities outlined in Section 11.
- **Physiologic use:** Adrenal replacement steroid doses including doses > 10 mg daily prednisone or equivalent is acceptable.
- **Prophylactic use** (e.g. for the prevention of acute infusion-related reactions) is prohibited, *except* prior to CT or MRI scan, or for the management of immune-related adverse events (irAEs) as outlined in Section 11.

10.4. Hematopoietic Growth Factors and Transfusional Support

- Packed red blood cell and platelet transfusions should be administered only if clinically indicated, and should be avoided during the first 28 days after the start of a patient's first avelumab infusion.
- Growth factors (granulocyte colony-stimulating factor or granulocyte-macrophage colony stimulating factor) are prohibited.

Patients who enter the study on stable doses of erythropoietin or darbepoietin may continue this treatment, and patients may start either drug during the study (if necessary, then ideally after the first 28 days of study treatment) at the discretion of the treating physician if clinically indicated.

10.5. Concomitant Radiotherapy

The potential for overlapping toxicities with radiotherapy and avelumab is currently unknown. Per eligibility criteria, prior therapeutic or palliative radiation therapy must be completed within 14 days prior to first dose of avelumab. After beginning study treatment, palliative radiotherapy is generally not recommended while receiving avelumab.

However, local radiotherapy of isolated lesions with palliative intent (e.g. bleeding, pain, compression, etc) is permitted if considered medically necessary by the treating physician. The irradiated area should be as small as possible. Irradiated lesions will be followed for disease progression but will not be accounted for in the evaluation of the response.

Subjects requiring palliative radiotherapy should be assessed for disease progression. If palliative radiotherapy is needed to control pain, the site(s) of disease causing pain should be present at baseline; otherwise, painful lesion(s) requiring radiotherapy should be considered as a sign of disease progression.

Subjects considered as having progressive disease are required to discontinue study therapy, or if appropriate, continue avelumab therapy as treatment beyond progression. Administration of additional avelumab to subjects who experienced disease progression at the time of palliative radiotherapy should follow guidelines specified in Section 9.7 (Treatment After Initial Evidence of Radiologic Disease Progression).

If palliative radiotherapy to bone metastases is required, then avelumab should be withheld for at least 1 week before, during, and 1 week after radiation. Subjects should be closely monitored for any potential toxicity during and after receiving radiotherapy, and adverse events considered related to radiotherapy should resolve to Grade \leq 1 prior to resuming avelumab.

Only non-target bone lesions that do not include lung tissue in the planned radiation field may receive palliative radiotherapy while on study treatment. Details of palliative radiotherapy should be documented in the source records and case report form (CRF). Details in the source records should include: dates of treatment, anatomical site, dose administered and fractionation schedule, and adverse events.

11. ADVERSE EVENT MANAGEMENT

11.1. Criteria for Holding Treatment for Adverse Event Possibly Related to Avelumab

No dose *reductions* of avelumab are permitted for the management of adverse events experienced by individual patients in this study.

As outlined below, *treatment delays* of up to 4 weeks (28 days) from last dose of avelumab are allowed.

Avelumab Treatment Should be DELAYED up to 4 Weeks (28 days) for the following Adverse Events if at least Possibly related to Avelumab:

- Any Grade \geq 3 drug-related adverse event, with the exception of alopecia and the following laboratory exceptions for lymphopenia, leukopenia, AST, ALT, and total bilirubin:
 - Grade 3 lymphopenia or leukopenia do not require a dose delay.
 - If subject had baseline AST, ALT, or total bilirubin within normal limits, then delay dosing for drug-related Grade \geq 2 liver function toxicity.
 - If subject had baseline AST, ALT, or total bilirubin that was Grade 1, then delay dosing for drug-related Grade \geq 3 liver function toxicity.
- Any AE, laboratory abnormality, or intercurrent illness regardless of severity or attribution to avelumab which, in the judgment of the investigator, warrants delaying investigational treatment with avelumab.

IMPORTANT:

The above list does NOT include other events which may require holding study treatment – even in cases of severity less than Grade 3 and regardless of attribution to study drug. Events such as Immune-Related Adverse Events (irAEs) of Special Interest, Infusion Reactions, Hypersensitivity, or Tumor Lysis Syndrome (if applicable) should be managed according to local institutional practice.

Dose delay criteria apply for drug-related adverse events – i.e. events which in the investigator's opinion are possibly, probably, or definitely related to avelumab. For adverse events deemed unlikely or unrelated to avelumab (e.g. related to disease), the medical judgement of the investigator should determine the extent to which a treatment delay is appropriate.

If avelumab treatment is delayed for > 4 weeks (28 days) from the last dose of avelumab, the subject must be permanently discontinued from study therapy, except as may be specified in Sections 9.4 and 11.3.

The window for a maximal 4 week (28 day) avelumab treatment delay begins on the calendar day of the most recent avelumab treatment preceding an event in question, and concludes on the calendar day that an immediately subsequent avelumab treatment is initiated.

In the event of multiple toxicities, treatment delay should be based on the worst toxicity observed.

In general, an adverse event related to study treatment that results in a dose delay should be present on the day of intended study treatment (i.e. a delayed toxicity that develops mid-cycle, but which is no longer present or has resolved to an acceptable grade on the day of intended dosing, generally does not require a delay in treatment).

Patients should be instructed to notify their study team at the first occurrence of any adverse symptom. In addition to dose delays according to protocol guidance, investigators are encouraged to employ best supportive care according to local institutional clinical practice.

Even if study drug dosing is interrupted, tumor scans and other visits, assessments and procedures should continue per protocol (i.e. per timeline in place prior to the dose interruption).

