11.2. Criteria for Resuming Treatment Held for Adverse Event Related to Avelumab

If a subject's avelumab treatment is held due to an adverse event that is possibly, probably or definitely related to avelumab, the subject may resume treatment with avelumab when the related adverse event resolves to \leq Grade 1 or to patient's baseline value, with the following exceptions:

- Subjects may resume treatment in the presence of Grade 2 fatigue or alopecia of any grade.
- Subjects who have not experienced a Grade 3 drug-related skin AE may resume treatment in the presence of Grade 2 skin toxicity
- Subjects with a Grade 2 AST/ALT or total bilirubin may resume treatment IF patient's respective baseline AST/ALT or total bilirubin was Grade 1 and the reason for patient's dose delay was NOT due to a 2 or more grade increase in AST/ALT or total bilirubin.
- Subjects with combined Grade 2 AST/ALT AND total bilirubin values meeting discontinuation parameters should have treatment permanently discontinued
- Drug-related pulmonary toxicity or colitis must have resolved to baseline before treatment is resumed
- Drug-related endocrinopathies adequately controlled with only physiologic hormone replacement may resume treatment.

The subject's baseline value is defined as the most recent value preceding initiation of the patient's first dose of avelumab.

In the event study treatment is held due to an event the investigator feels is unlikely related or not related to avelumab (e.g. hold study drug per investigator discretion in order to evaluate appropriate attribution to disease versus drug), then resumption of avelumab may proceed according to the medical judgement of the investigator (with maintained accordance to other protocol sections).

If treatment is delayed > 4 weeks (28 days) from the last dose of avelumab, the subject must be permanently discontinued from study therapy, except as may be specified in Sections 9.4, 11.2 and 11.7.

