11.6. Management of Immune-Related Adverse Events (irAEs)

Since inhibition of PD-L1 stimulates the immune system, immune-related adverse events (irAEs) may occur. **Any adverse event judged by the investigator to be possibly, probably or definitely immune-related should be managed according to the guidance in this section for the management of immune-related adverse events, except for circumstances in which local or other standards known to exist are felt by the investigator to present a more medically appropriate course of management.**

Treatment of irAEs is mainly dependent upon severity (NCI-CTCAE grade):

- Grade 1 to 2: treat symptomatically or with moderate dose steroids, more frequent monitoring
- Grade 1 to 2 (persistent): manage similar to high grade AE (Grade 3 to 4)
- Grade 3 to 4: treat with high dose corticosteroids

Some potential irAEs described with anti-PD-L1 drugs such as avelumab may be similar to toxicities related to disease (e.g. diarrhea related to adenocarcinoma of the small intestine). In general: Rule out non-inflammatory causes; if non-inflammatory cause is identified, treat accordingly and continue study treatment according to protocol.

Corticosteroids are a primary therapy for immuno-oncology drug-related adverse events. Patients treated for irAEs with IV steroids may be switched to an equivalent dose of oral corticosteroids (e.g. prednisone) at start of tapering or earlier, once sustained clinical improvement is observed. Lower bioavailability of oral corticosteroids should be taken into account when switching to the equivalent dose of oral corticosteroids.

MANAGEMENT of GASTROINTESTINAL IMMUNE-RELATED ADVERSE EVENTS (irAEs)		
Diarrhea / Colitis	Management	Follow-Up

Grade 1
 
Diarrhea: < 4 stools/day over baseline
 
Colitis: Asymptomatic
	
 • Continue avelumab therapy per protocol. • Symptomatic treatment (e.g. loperamide). 	
 • Close monitoring for worsening symptoms. • Educate patient to immediately report worsening. 
If worsens:
 
 • Treat as Grade 2, or Grade 3 to 4.

MANAGEMENT of GASTROINTESTINAL IMMUNE-RELATED ADVERSE EVENTS (irAEs)		
Diarrhea / Colitis	Management	Follow-Up

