
Grade 2
 
AST or ALT > 3.0 to ≤ 5 x ULN and/or total bilirubin > 1.5 to ≤ 3 x ULN
	
 Delay avelumab therapy per protocol. Increase frequency of monitoring to every 3 days. 	
If returns to Grade ≤ 1:
 
 Resume routine monitoring, resume avelumab therapy per protocol. 
If elevations persist > 5 to 7 days or worsen:
 
 Treat as Grade 3 or 4.

Grade 3-4
 
AST or ALT > 5 x ULN and/or total bilirubin > 3 x ULN
	
 Permanently discontinue avelumab therapy. Increase frequency of monitoring to every 1 to 2 days. 1.0 to 2.0 mg/kg/day methylprednisolone IV or IV equivalent. Add prophylactic antibiotics for opportunistic infections. Consult gastroenterologist/hepatologist Consider obtaining MRI/CT scan of liver and liver biopsy if clinically warranted. 	
If returns to Grade ≤ 1:
 
 Taper steroids over at least 1 month. 
If does not improve in > 3 to 5 days, worsens or rebounds:
 
 Add mycophenolate mofetil 1 gram (g) twice daily (BID). If no response within an additional 3 to 5 days, consider other immunosuppressants per local guidelines.
MANAGEMENT of RENAL IMMUNE-RELATED ADVERSE EVENTS (Renal irAEs)		
Renal Disorder	Management	Follow-Up

Grade 1
 
Creatinine increased > ULN to 1.5 x ULN
	
Continue avelumab therapy
	
Continue renal function monitoring
 
If worsens:
 
Treat as Grade 2 to 3 or 4.

Grade 2 to 3 Creatinine increased > 1.5 and ≤ 6 x ULN
	
Withhold avelumab therapy Increase frequency of monitoring to every 3 days 1.0 to 2.0 mg/kg/day prednisone or equivalent. Add prophylactic antibiotics for opportunistic infections Consider renal biopsy
	
If returns to Grade ≤1: Taper steroids over at least 1 month, and resume avelumab therapy following steroids taper. If worsens: Treat as Grade 4.

Grade 4 Creatinine increased > 6 x ULN
	
Permanently discontinue avelumab therapy Monitor creatinine daily 1.0 to 2.0 mg/kg/day prednisone or equivalent. Add prophylactic antibiotics for opportunistic infections Consider renal biopsy Nephrology consult
	
If returns to Grade ≤1: Taper steroids over at least 1 month.

MANAGEMENT of ENDOCRINE IMMUNE-RELATED ADVERSE EVENTS (irAEs):		
Endocrine Disorder	Management	Follow-Up

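### For Grade 3-4 liver toxicity that is drug-related and possibly immune-related, Sections 11.1 and 11.2 read alone permit re-dosing where the 11.6 hepatic table stops avelumab for good, and no sentence says which governs

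*Combined protocol and SAP*

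**What the plan says.** **Holding (11.1).** Under the instruction "Avelumab Treatment Should be DELAYED up to 4 Weeks (28 days) for the following Adverse Events if at least Possibly related to Avelumab", a patient with normal baseline liver tests is held for drug-related toxicity of Grade 2 or higher. For the others: "If subject had baseline AST, ALT, or total bilirubin that was Grade 1, then delay dosing for drug-related Grade" 3 or higher. Neither rule has an upper grade limit. The 28-day window "begins on the calendar day of the most recent avelumab treatment preceding an event in question". A toxicity that appears mid-cycle but "has resolved to an acceptable grade on the day of intended dosing, generally does not require a delay in treatment".

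**Resuming (11.2).** After a hold for a related event, "the subject may resume treatment with avelumab when the related adverse event resolves to" Grade 1 or less, or to the patient's baseline. The listed exceptions include no stop for Grade 3-4 liver events. One exception does order a permanent stop, for combined Grade 2 AST/ALT and bilirubin, but it relies on thresholds that the protocol never gives.

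**Immune-related events (11.6).** Any event judged at least possibly immune-related falls under this instruction: "managed according to the guidance in this section for the management of immune-related adverse events, except for circumstances in which local". The exception applies where the investigator thinks that local standards, or others, suit the patient better. At AST or ALT above 5 x ULN, or total bilirubin above 3 x ULN, the hepatic table says: "Permanently discontinue avelumab therapy". Its follow-up column describes a steroid taper and no return to treatment.

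**Routing.** The note in 11.1 says that immune-related events of special interest "should be managed according to local institutional practice". Section 14.5.12 counts every suspected immune-related event as one of special interest. Sections 11.2 and 14.5.12 both cite a Section 11.7, but Section 11 ends at 11.6.

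**The concern.** This is a stopping rule for patient safety, and safety is one of the two primary objectives (Section 3.1). An investigator who sees ALT above 5 x ULN, thinks avelumab may be the cause, and turns to the sections titled for holding and resuming treatment finds a complete pathway: hold, wait for recovery, re-dose. Nothing there says to ask whether a liver event is immune-related, or to go to 11.6 if it is. The hepatic table treats the same laboratory values as the end of treatment. Which action the patient gets can therefore depend on which subsection is opened. What is at stake is re-exposure after a Grade 3 or 4 liver event that the protocol elsewhere regards as a permanent stop.

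**Working it through.** The plan states no figure to reproduce on this point. The check is a comparison of texts, followed by a count of how often the case could arise.

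**Step 1: one patient, two rules.** Take a patient with normal or Grade 1 baseline and a liver event above the 11.6 Grade 3-4 limits, judged at least possibly related to avelumab and at least possibly immune-related.

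| | 11.1 and 11.2 | 11.6 hepatic table |
|---|---|---|
| Action at onset | Hold | Stop permanently |
| After recovery to Grade 1 or baseline | May resume if the next dose is within 28 days of the last | Taper steroids; no resumption given |
| Recovered before the dosing day | Generally no delay | Stop permanently |

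The window is 28 days from the last dose. With a 14-day cycle, that leaves 28 - 14 = 14 days after the scheduled dose.

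**Step 2: does 11.2 really contemplate these patients?** Yes. Its liver exception allows resumption at Grade 2 for a Grade 1 baseline, unless the hold was for a rise of two or more grades. From a Grade 1 baseline, the 11.1 liver rule triggers only at Grade 3, and 3 - 1 = 2 grades. So 11.2 has these patients in view. It makes them recover further before resuming but does not stop them.

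**Step 3: combined Grade 2 elevation.** Section 11.2 stops permanently on undefined thresholds. The 11.6 table delays for Grade 2 AST/ALT and/or bilirubin, and moves to Grade 3-4 management only if the elevation lasts more than 5 to 7 days or worsens. Section 5.2 admits patients with liver metastases at AST/ALT up to 5 x ULN. That is the top of the table's Grade 2 band (above 3 to 5 x ULN), so the missing thresholds matter from study entry.

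**Step 4: how often.** Section 4.5 gives treatment-related Grade 3 or higher events in 717 subjects at 10 mg/kg: AST increased 4, ALT increased 3, autoimmune hepatitis 4. Autoimmune hepatitis is immune-related by name, so 11.6 plainly claims it; I leave it out of the main count. The overlap between AST and ALT cases is not reported, so the count is 4 (full overlap) to 4 + 3 = 7 (none).

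Expected patients = 25 x k/717:
- k = 4: 4/717 = 0.56%, and 25 x 4/717 = 0.14
- k = 7: 7/717 = 0.98%, and 25 x 7/717 = 0.24
- with autoimmune hepatitis and no overlap, k = 11: 11/717 = 1.53%, and 25 x 11/717 = 0.38

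The rules diverge only if recovery comes in time for a dose within 28 days. The documents do not give that share. Assuming f = 25% to 75%, expected patients = 25 x (k/717) x f runs from 25 x (4/717) x 0.25 = 0.03 to 25 x (7/717) x 0.75 = 0.18. The chance of at least one, 1 - (1 - f x k/717)^25, runs from 3.4% to 16.8%.

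Even this counts events that recover in time, not collisions. A collision also needs an event that is at least possibly immune-related and an investigator who follows 11.1 and 11.2 instead of 11.6.

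**The case against.** The strongest reply is that Section 11 has a scope structure, not a contradiction. Sections 11.1 and 11.2 are general rules for holding and resuming. Section 11.6 is the specific rule for immune-related events and claims anything at least possibly immune-related. Section 9.4 makes discontinuation mandatory for adverse-event reasons given in Section 11, and 9.3 ends treatment when such a criterion applies. Permission to resume does not cancel a required stop, and the mid-cycle sentence concerns delay only. Section 11.1 also warns that its list is incomplete and names immune-related events. Moreover, the hepatic table's steroid taper lasts at least a month after return to Grade 1, so a patient managed under 11.6 would normally pass the 28-day limit anyway.

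Most of this stands. It shows that a reader of all of Section 11, with 9.3 and 9.4, can reach the stop. It does not show that the reader is led there. The 11.1 note that sets immune-related events apart sends them to local practice as the default; 11.6 allows local standards only as an exception. Neither 11.1 nor 11.2 refers liver events to 11.6. If 11.7 is a misnumbered 11.6, the mention in 11.2 concerns only the 28-day limit. Section 11.2 also sets resumption rules for lung, colitis, skin and endocrine events that 11.6 tabulates, so the sections overlap without a stated order.

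A reader might infer something broader: that every drug-related Grade 3-4 liver event must stop under 11.6 and that 11.1 and 11.2 contradict this. The documents do not support that. The table is confined to immune-related events. A drug-related event judged not immune-related falls outside it, and hold-and-resume is then the only rule.

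**Conclusion.** The point holds in a limited form. For Grade 3-4 liver toxicity that is both drug-related and at least possibly immune-related, 11.1 and 11.2 read alone permit re-dosing that the 11.6 hepatic table rules out. The rest of the protocol implies that 11.6 controls, but precedence is left to inference, and the local-practice note and the two dead references weaken that inference. It would go too far to say that the protocol as a whole authorises re-dosing after such an event.

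The case is rare: 0.14 to 0.24 Grade 3 or higher AST/ALT events expected in 25 patients, as an upper bound on collisions at those rates. This assumes that the rates in the 717-subject pool carry over. That pool is other tumor types, and Grade 3 or higher bilirubin elevation is not listed in it, so the rate here may differ. The recovery shares behind the 0.03 to 0.18 range are assumptions.

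The reason to act is the consequence for a patient, not the frequency. Sample size, the response-rate rule and the analysis are unaffected. The undefined combined-elevation limit and the misnumbered references would by themselves be missing detail and clerical error.

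**What to change.** Amend the text as follows.

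1. In 11.1 and 11.2, state that the 11.6 hepatic table governs any liver event at least possibly immune-related, so Grade 3-4 means permanent discontinuation, and that neither resumption under 11.2 nor the mid-cycle sentence in 11.1 overrides an 11.6 stop.
2. In the 11.1 note, replace the local-practice default for immune-related events with a reference to 11.6 and the exception it already contains.
3. Correct 11.7 to 11.6 in 14.5.12 and 11.2. In 11.2, the sponsor should confirm that an exception to the 28-day limit for immune-related events is intended, and otherwise delete it.
4. Have the sponsor set one limit for combined AST/ALT and bilirubin elevation, used in both 11.2 and 11.6, that allows for patients who enter with AST/ALT up to 5 x ULN.

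The cost is amendment text, with no added procedures or visits. The downside is that an occasional patient will stop avelumab earlier than under 11.1 and 11.2 read alone.

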Requirement for 10 mg per day or greater prednisone or equivalent for more than 12 weeks for reasons other than hormonal replacement for adrenal insufficiency Persistent Grade 2 or 3 irAE lasting 12 weeks or longer	
 • Permanently discontinue avelumab therapy • Specialty consult 	

Abbreviations: ACTH=adrenocorticotrophic hormone; ADL=activities of daily living; ALT=alanine aminotransferase; AST=aspartate aminotransferase; BNP=B-type natriuretic peptide; CK-MB=creatinine kinase MB; CT= computed tomography; FSH=follicle-stimulating hormone; GH=growth hormone; IGF-1=insulin-like growth factor 1; irAE=immune related adverse event; IV=intravenous; LH=luteinizing hormone; MRI=magnetic resonance imaging; NCI CTCAE=National Cancer Institute Common Terminology Criteria for Adverse Events; PRL=prolactin; T4=thyroxine; TSH=thyroid stimulating hormone; ULN=upper limit of normal.

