14.5.12 Adverse Events of Special Interest (AESIs)

Any adverse event that is suspected to be a potential immune-related adverse event (irAE) is considered an AE of special interest (AESI). Specific guidance for the management of irAEs is provided in Section 11.7. AESIs are reported according to the general AE reporting rules specified in Section 14.5.

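### Section 11.1's 28-day stop rule blocks the restart after a steroid taper that five branches of Section 11.6 direct, and one hypophysitis presentation gets opposite dosing instructions

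*Combined protocol and SAP*

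**What the plan says.** Section 11.1 allows delays of up to 28 days. Beyond that, the rule is: "If avelumab treatment is delayed for > 4 weeks (28 days) from the last dose of avelumab, the subject must be permanently discontinued". It then names its only exceptions: "except as may be specified in Sections 9.4 and 11.3". The clock starts at the last infusion before the event, not at onset or at the missed dose: "The window for a maximal 4 week (28 day) avelumab treatment delay begins on the calendar day of the most recent avelumab treatment". Section 11.1 adds that, in general, "an adverse event related to study treatment that results in a dose delay should be present on the day of intended study treatment". Section 11.2 repeats the stop rule with a different list of exceptions: "except as may be specified in Sections 9.4, 11.2 and 11.7".

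Section 11 ends at 11.6, the irAE section. Section 14.5.12 still uses the other number: "Specific guidance for the management of irAEs is provided in Section 11.7".

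In 11.6, five branches direct resumption only after a steroid taper of at least 1 month, and the taper follows improvement to Grade 1 or lower:

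- initial Grade 3 diarrhea or colitis
- initial Grade 3 rash
- Grade 2 pneumonitis
- Grade 2 to 3 renal events
- any other Grade 2 or first Grade 3 irAE

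The table for other irAEs also sets its own permanent-stop limits: "Persistent Grade 2 or 3 irAE lasting 12 weeks or longer", and "Requirement for 10 mg per day or greater prednisone or equivalent for more than 12 weeks" for reasons other than adrenal replacement.

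The hypophysitis row of the endocrine table has two lines. One continues avelumab for mild symptoms with a normal MRI. The other withholds it for mild symptoms, an abnormal MRI, or both.

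**The concern.** Describing safety is one of the two primary objectives (Section 3.1), and these rules decide who is re-dosed after a steroid-treated irAE. The conflict runs one way. Stopping at day 28 satisfies 11.1 and is compatible with 11.6, which is guidance that leaves the investigator some latitude. Restarting after the taper, as 11.6 directs, breaks the mandatory wording of 11.1. A patient whom 11.6 would restart therefore either loses treatment for good or is restarted as a departure from 11.1. What is at stake is drug exposure, re-exposure after irAEs and recorded discontinuations, which may be handled differently from one patient to the next.

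**Working it through.** No design figure depends on this rule. The plan's own numbers here are the 28-day cap (11.1) and the 14-day dosing interval (9.2).

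**1. What the cap allows.** 28/14 − 1 = 1 missed dose.

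**2. Can a taper fit at all?** The protocol does not convert 1 month to days, so I take 28 to 31 days as an assumption. Counting the last dose as day 0, the latest taper start that fits is 28 minus the taper length:

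| Taper (days) | Latest start that fits |
|---|---|
| 28 | 28 − 28 = day 0 |
| 30 | 28 − 30 = day −2 |
| 31 | 28 − 31 = day −3 |

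A 28-day taper fits only if it starts on the day of the last infusion. Longer tapers never fit.

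**3. The general case in 11.1.** The event is still above Grade 1 on the next dosing day, so the taper starts on day 14 or later. Earliest restart = 14 + days to reach Grade 1 + taper length.

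- No further time to improve: 14 + 28 = day 42 to 14 + 31 = day 45, which is 14 to 17 days past the cap.
- Three to 7 further days to improve (illustrative): 14 + 3 + 28 = day 45 to 14 + 7 + 31 = day 52.

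Persistent Grade 1 to 2 rash meets the same obstacle if steroids are given, but there the steroid is only to be considered, so I do not count it among the five.

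**4. Do the exceptions help?**

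- 9.4 (cited in 11.1 and 11.2) lists reasons to discontinue and refers adverse events back to Section 11. It extends nothing.
- 11.3 (cited in 11.1) covers infusion reactions: rate changes, interruption, and permanent stop at Grade 3 or 4. It contains no longer delay.
- 11.7 (cited in 11.2) does not exist, but 14.5.12 identifies it as the irAE guidance, which is now 11.6. Read that way, 11.2 exempts irAE holds and 11.1 still does not.

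**5. Evidence of intent.** The 12-week limits in 11.6 are 12 × 7 = 84 days, or 84/28 = 3 times the cap. The same table withholds drug for Grade 2 and first Grade 3 irAEs, so its limits presuppose holds longer than 28 days.

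**6. How many patients?** Section 4.5 reports treatment-related events in 717 patients at this dose. Grade 3 or higher colitis occurred in 2. Diarrhea and rash are absent from the Grade 3 or higher events seen in at least 2 patients, so if that list is complete each occurred in at most 1. Together that is at most 2 + 1 + 1 = 4 of 717 (0.56%), and 25 × 4/717 = 0.14 expected patients. As an outer figure, all Grade 3 or higher treatment-related events were 77 of 717, and 25 × 77/717 = 2.7 patients. That figure includes infusion reactions and enzyme rises outside these branches. Follow-up there was only at least 4 weeks, and no Grade 2 irAE rates are given. The bound also omits Grade 2 diarrhea or colitis that persists or recurs, which 11.6 treats as Grade 3 or 4.

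**7. Hypophysitis.** Mild symptoms with a normal MRI satisfy the continue line in full. They also satisfy the withhold line, because mild symptoms alone are enough there.

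**The case against.** The best case on the other side is that this is a matter of outdated section numbers and not a conflict of design. With 11.7 read as 11.6, Section 11.2 already exempts irAE holds. If every number has slipped by one, 11.3 in Section 11.1 becomes 11.2, and the chain from 11.1 to 11.2 to 11.6 is complete. Section 11.1 also carries a prominent note that its list does not cover irAEs of special interest and sends them to local practice, and 11.6 lets the investigator prefer local standards. The literal rule errs toward less re-exposure.

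Much of this is right about intent. A reader might infer that 11.2 bars the restart as firmly as 11.1, or that 11.3 was meant to be 11.6. The documents do not support either: 14.5.12 points 11.2 at the irAE guidance, and the intended target of 11.3 is uncertain. What remains is that 11.1 as written has no exception that reaches an irAE hold. The local-practice wording governs how an event is managed and does not lift the mandatory stop. Re-treatment under 9.7 is not a way round, since it requires radiologic progression after stopping and IRB approval.

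A reader might also count overruns for events that settle before day 14. Section 11.1 says that a toxicity resolved to an acceptable grade by the dosing day generally needs no delay, so the firm figure is the day-14 case.

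The hypophysitis overlap is a separate matter in one row of guidance. It should not raise the weight given to the stop rule.

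**Conclusion.** The point holds, at minor to moderate severity. For an irAE still above Grade 1 on day 14, the restart directed by five branches of 11.6 falls at least 14 to 17 days beyond the limit in 11.1, and no exception in 11.1 covers it. The one numerical assumption is a month of 28 to 31 days. The hypophysitis row gives two opposite orders for one presentation.

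Few of the 25 patients are likely to be affected: well under one is expected for the Grade 3 gastrointestinal and rash branches, subject to the caveats above, while the Grade 2 branches cannot be sized from the documents. A reader might infer damage to the efficacy analysis, but the documents do not show it. Scans continue during holds (9.2 and 11.1), Section 17.3 plans no analysis of re-exposure or discontinuation reason, and power, type I error, sample size and endpoint definitions are untouched.

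**What to change.** 1. Change 11.7 to 11.6 in Sections 11.2 and 14.5.12.
2. Add 11.6 to the exception in 11.1, and state that irAE holds managed with a steroid taper under 11.6 are exempt from the 28-day cap. The sponsor should confirm that the 12-week stopping limits bound all such holds, because they sit in the table for irAEs not covered elsewhere and do not plainly reach gastrointestinal, rash, pneumonitis and renal holds.
3. Reword the hypophysitis withhold line so that it no longer overlaps the continue line, with the threshold confirmed by the sponsor's clinicians.

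The cost is one protocol amendment, which under Section 16.2 needs approval by the drug supplier and the IRB before local implementation and submission to the FDA as necessary. It adds no visits, procedures or patients.
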